5.2 Preparation for Treatment

Patients will receive best MM for intracerebral and/or intraventricular hemorrhage as determined by the attending physician as specified in the companion INVEST Feasibility study. All attending physicians will follow current AHA guidelines for the treatment of ICH⁵. Reversible coagulopathies at presentation will be corrected as determined by the attending physician managing the patient. Ventricular drains will be placed as deemed necessary by the clinical care team to manage ICPs. Apollo / Artemis MIES will be performed under general anesthesia. The subject should be prepared for the planned intervention according to standard hospital procedures. Apollo / Artemis MIES will be performed as described below (5.5)

5.3 Medication during Intervention

Medications may be administered during the procedure as determined by the attending anesthesiologist and/or interventionist in accord with established standard procedural management.

5.4 Devices and Equipment

In addition to the Apollo System and Artemis Device, other devices required for the procedure are listed in Table 5.

Standard Cranial Access Devices and	All FDA cleared cranial access systems and
Endoscopy Sheath	suitably sized endoscopy sheaths (19-22F)
	will be allowed in the study
Neuronavigation System	All FDA cleared neuronavigation systems
	will be allowed in the study
Neuroendoscopy System	All FDA cleared neuroendoscopy systems
	(e.g. Storz Lotta) which incorporate a
	working channel that will accommodate
	either the 1.5, 2.1, or 2.8 mm Artemis
	Device will be allowed in the study
Penumbra Aspiration Systems	The Aspiration Pump and canister for all
	FDA cleared or CE marked (as
	applicable) Penumbra Aspiration Systems
	will be allowed in the study
Intra-Operative or Extra-Operative CT	All FDA cleared computed tomography or
Monitoring	cone beam computed tomography systems
	will be allowed in the study.

Table 5: Devices that are used during the Apollo / Artemis MIES procedure

The specific types of devices used in each Apollo / Artemis MIES procedure will be recorded in the patient CRF.

5.5 Procedural Protocol

Appropriately protocoled (depending on the institution and neuronavigation units) MR or CT imaging studies will be uploaded into the neuronavigation software (e.g., iPlan Net, Brainlab, Feldkerchin Germany) for procedural planning and guidance. A trajectory will be selected by the operator that is both technically feasible and allows access to the longest possible axis of the cerebral hematoma (for ICH) or optimal position within the ventricular system (for IVH).

Patients will be placed supine upon the procedural table, and a sterile field prepared. An external localization array or other neuronavigation localization mechanism (e.g. Skull Reference Base with Skull Reference Array with Reflective Marker Spheres, Brianlab) will be placed for registration. Following registration, a second sterile field will be prepared over the region of the cranial access. A burr hole or minicraniotomy will then be created in a standard manner of a size large enough to accommodate the selected endoscopy sheath. A localization array (e.g., Instrument Adapter Clamp with Instrument Adapter Array, Brainlab) will be attached to the selected neuroendoscopic sheath (e.g., Aesculap Inc, Center Valley, PA) and registered to the navigation system. The sheath will then be advanced using neuronavigation into the targeted landing zone within the distal aspect of the hematoma and the inner obturator removed. The sheath will then be stabilized (e.g., manually stabilized, mechanically stabilized, or peeled away and stapled down) into position. The

neuroendoscope (e.g., Lotta, Karl Storz, Tuttlington, Germany) will then be inserted into the sheath and under direct visualization the Apollo Wand or Artemis Device will be placed through the working channel of the trocar. The sheath will be irrigated at the discretion of the operator using the irrigation port of the endoscope and the irrigant will be intermittently aspirated with the Apollo system or Artemis Device until a clear working view is created within the sheath that allows visualization of the surgical field at the sheath tip. When organized hematoma is visualized at the tip of the sheath, the Apollo Wand or Artemis Device will be advanced under direct visualization to, or just beyond the tip of the sheath and actuated to evacuate the blood products. If the working view becomes obscured by blood products within the sheath, additional irrigation and aspiration will be performed intermittently to clear the field. When all blood products are cleared from the working field, the sheath will be retracted serially and the procedure repeated. The position of the sheath will be continually monitored directly using the neuronavigation system. After the evacuation is completed, the neuroendoscopic trocar and Apollo Wand or Artemis Device will be removed. An intraoperative CT (e.g. dynaCT, Siemens, Medical Imaging, Erlangen, Germany) will then be performed using cone-beam CT, an intraoperative or portable conventional CT unit, or the OR room will be held open for re-operations and the patient may be scanned on a conventional departmental CT unit with the option to immediately return to the OR room if necessary. The control CT will function to confirm adequate hematoma evacuation and to assess for any complications (e.g., re-bleeding, hydrocephalus, increased mass effect).

Additional evacuation will be performed as specified above at the discretion of the operator, based upon the data from the CT. After the hemorrhage evacuation is completed, the sheath will be removed and the cranial access site will be closed in a standard manner.

5.6 Post-Procedure Care

All patients will receive best MM for ICH as determined by the attending physicians of the clinical team:

- General medical management according to AHA guidelines⁵
- Admission to monitored or intensive care unit for at least 24 hours
- Close monitoring of BP and glucose with treatment according to AHA guidelines⁵
- Follow-up imaging study required in any patient with neurologic deterioration

An immediate post-procedural CT scan will be obtained in all patients after Apollo / Artemis MIES. Neurological and functional exams will be conducted within 24 hours (+/- 12 hours) of the procedure. A CT (preferred) or MR scan will also be obtained 7 days after randomization in both groups. Additional imaging will be obtained at the discretion of the managing service based upon clinical data and established institutional standard of care.

5.6 Recovery

The subject will be recovered from the procedure and discharged from the hospital as per standard practices.

5.6.1 Discharge

At discharge, the following will be completed by a qualified member of the research or clinical care team: a focused physical exam, a neurological exam (including GCS, NIHSS and mRS) and a review of any adverse events. If discharge occurs before 7 days after randomization, the discharge clinical examinations will substitute for the 7-day clinical evaluation and a standard of care CT (preferred) or MR will be obtained at that time.

5.7 Hospital Costs

For each subject, overall costs will be collected for the initial hospitalization during which study enrollment took place. These costs will include device costs (the market price for each device), materials used to treat the hemorrhage, and number of days spent in the hospital (ICU and non-ICU length of stay). In summary, the total amount billed and the total amount reimbursed will be assessed.

5.8 Follow-Up Examination

5.8.1 Clinical

Several clinical outcome measures were selected for this study. These were chosen on the basis of their reliability, familiarity to the neurologic community, adaptability for use in patients who have had a stroke, and comparability to end points used in other trials of intracranial hemorrhage. All scores will be recorded in source documentation and entered into the electronic case report forms.

- 1. modified Rankin Scale (mRS, Appendix 4): mRS is an overall assessment of global handicap. In the original Rankin Scale, a score of zero indicates the absence of symptoms and a score of 5, severe disability. The modified Rankin Scale adds a score of 6 for fatal outcomes. A historical mRS will be obtained to assess the patient's level of function prior to the ICH. The score will be repeated as specified in Table 1.
- 2. The National Institutes of Health Stroke Scale (NIHSS, Appendix 5) is a 42-point scale that quantifies neurologic deficits in 11 categories. Normal function without neurologic deficit is given a score of zero. NIHSS should be done by a certified examiner as close to the specified times as possible.
- 3. EQ-5D-5L (Appendix 6) is a standardized instrument for use as a measure of health outcome. Applicable to a wide range of health conditions and treatments, the questionnaire provides a simple descriptive profile and a single index value for health status.

All day 7, discharge, day 30, day 90 and day 180 clinical outcome measures will be assessed by a qualified member of the research or clinical team either in person at a clinic visit, by phone or by mailed questionnaire. The schedule of neurological assessments is listed in Table 1. At each visit, the patient's medical record will be surveyed for any new or interim neurological adverse or serious adverse events. In addition, the patient or LAR will be asked about any interim neurological adverse or serious adverse events. The subject or LAR will also be specifically asked about any interim neurosurgical procedures.

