5.8.3 Serious Adverse Events

All serious adverse events occurring during the 180-days of study participation will be recorded. Adverse events and serious adverse events are critical endpoints and will be assessed as they occur and at the scheduled clinic visits. A serious adverse event is one that is fatal or life-threatening, is permanently or substantially disabling, requires or prolongs hospitalization, or any event that the treating clinician judges to be a significant hazard, contraindication, side effect, or precaution. For each recorded serious adverse event, the patient's attending physician will be asked to classify the causal relationship of the event to the study treatment as probable, possible, unlikely, and unrelated. Detailed form and narrative reports of the following specific adverse events will be obtained:

- Death (all cause) within 30 days of enrollment
- Death within 7 days of enrollment: Immediate peri-procedural death
- Symptomatic Re-Hemorrhage or New Hemorrhagic Event: any new intracranial hemorrhage or increase in size of pre-existing hemorrhage (IPH, IVH or extra-axial bleed) within 30 days associated with an increase of 4 or more points on the NIHSS or GCS increase ≥2 persisting for at least 24 hours and/or requiring emergency surgical decompression or resulting in death^{5, 6}.
- Symptomatic Evolution of Peri-hematomal Edema: Edema with increased mass effect or uncontrolled ICPs within 30 days requiring emergency surgical decompression NOT related to new or increased hemorrhage (i.e. edema related) associated with an increase of 4 or more points on the NIHSS or GCS increase ≥2 persisting for at least 24 hours, requiring emergency surgical decompression or resulting in death.
- Symptomatic Ischemic Stroke: A new ischemic stroke (ipsilateral, contralateral; contiguous with bleed/operative site or remote; cortical, subcortical or perforator distribution) within 30 days associated with an increase of 4 or more points on the NIHSS or GCS increase \geq 2 persisting for at least 24 hours, requiring emergency surgical decompression or resulting in death.
- Surgical complications related to Apollo /Artemis MIES: Surgical site infection, brain abscess or confirmed meningitis, or documented complication(s) deemed specifically related to the procedural anesthetic (medication, access or intubation related) within 30 days.

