16.2 Reporting and Review of Adverse Events

To provide for consistent reporting of adverse events, serious and non-serious adverse events will be recorded on the Adverse Event CRF. Non-serious adverse events will be recorded from randomization through Day 7 or hospital discharge (whichever occurs first). Serious adverse events will be recorded from randomization through the end of study (i.e., 180 day final follow-up visit, death, or withdrawal of consent).

In order to ensure prompt reporting of adverse events, we require that all adverse events (as well as all related study data) be entered into the REDCap web-based database (REDCap) within five working days of their becoming aware of the event during the initial admission. For all serious adverse events (SAEs), we require that they be reported in the REDCap within 24 hours of the study site staff first being made aware of the occurrence of the SAE. The 24-hour reporting requirement for SAEs applies to all study phases.

Reporting of serious or life-threatening adverse events will trigger notification of the event to the Medical Monitor (MM). The MM will conduct an independent review of these specific SAE. If the MM believes the adverse event is serious, unexpected and either definitely, probably, or possibly related to the investigational device(s) and/or study procedures, the TOC staff will forward a Safety Report (pre-filled with as much data as possible) to the clinical site Investigator to be completed with any additional information that may be relevant to the SAE. The Safety Reports will be included in the reports prepared for the DSMB. The principal investigator, at each clinical site, will be responsible for reporting to his/her own IRB/EC according to individual IRB/EC policies. After the submission of the initial Safety Report, the principal investigator at the corresponding clinical site will be responsible for obtaining follow-up information about the event, and reporting it to the TOC.

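### On its natural reading, Section 5.8.1 looks only for neurological events at the follow-up contacts, which is narrower than the requirement to record every SAE to day 180; non-neurological SAEs after discharge may be under-ascertained.

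*Combined protocol and SAP*

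**What the plan says.** Section 5.8.1 lets the follow-up outcome measures be taken "either in person at a clinic visit, by phone or by mailed questionnaire". It then sets out how events are found. For the chart: "At each visit, the patient's medical record will be surveyed for any new or interim neurological adverse or serious adverse events". For the interview: "the patient or LAR will be asked about any interim neurological adverse or serious adverse events". One further prompt follows: "The subject or LAR will also be specifically asked about any interim neurosurgical procedures".

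Other sections set a wider requirement. Section 5.8.3 states: "All serious adverse events occurring during the 180-days of study participation will be recorded". Its next sentence has AEs and SAEs assessed both when they happen and at the scheduled clinic visits, with no restriction by body system. Section 16.2 agrees: "Serious adverse events will be recorded from randomization through the end of study", meaning the 180-day visit, death or withdrawal of consent. Table 1 has an unrestricted Adverse Events row marked at 1, 3 and 6 months.

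The events that Section 5.8.3 singles out for detailed reporting include, within 30 days, "Surgical site infection, brain abscess or confirmed meningitis, or documented complication(s) deemed specifically related to the procedural anesthetic". At discharge, Section 5.6.1 has the team review adverse events of any kind. Sections 16 and 16.2 stop recording non-serious events at day 7 or discharge, whichever is earlier.

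**The concern.** The stated search is narrower than the stated requirement. A coordinator working from Section 5.8.1 would look for neurological events in the chart, ask the patient or LAR about neurological events, ask about neurosurgery, and stop. Nothing there prompts for a hospital admission, a wound infection, sepsis or pneumonia. A readmission is an SAE by definition under Section 16.1, and surgical site infection is a specified event under Section 5.8.3. Neither need be neurological, and both can first appear after discharge.

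Additional safety data are part of the registry's primary objective, and Section 7.5.1 reports the number and percentage of patients with each event, also by relationship to procedure or device. Under Section 7.5.2.1 the DSMB receives periodic reports of all AEs and SAEs drawn from the same data. With one arm, no internal comparator would show that the count was incomplete.

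**Working it through.** **Step 1. Set the provisions side by side.**

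| Place | Scope | What it tells a site to do |
|---|---|---|
| 5.6.1, discharge | Any adverse event | Review events at discharge |
| 5.8.1, follow-up contacts | Neurological events (natural reading), plus neurosurgical procedures | Survey the record; ask the patient or LAR |
| 5.8.3 | All SAEs to day 180 | Assess as they occur and at clinic visits; no method given |
| Table 1 | Adverse events, unrestricted, at 1, 3 and 6 months | No method given |
| 8.1 | Any SAE that caused a missed visit | Complete an AE form; missed visits only |
| 16, 16.2 | All SAEs to end of study | Report within 24 hours of site awareness |
| 21 | 100% of SAEs | Verify against source; not described as a search for unreported SAEs |

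Only Section 5.8.1 says what to look for and what to ask when a follow-up contact takes place as planned. Section 5.8.3 and Table 1 create a duty to assess without supplying a method. The 24-hour rule begins only when the site already knows of the event. Section 5.8.3 also speaks of clinic visits, whereas Section 5.8.1 allows phone and mail, where the wording of the question matters most.

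**Step 2. Test the wording.** The key phrase can be read in two ways.

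- Reading A: *neurological* governs both nouns, so only neurological AEs and neurological SAEs are sought.
- Reading B: the phrase means neurological AEs, or else SAEs of any kind.

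Reading A is the more natural, and the following sentence on neurosurgical procedures points the same way. Under B there is no conflict on SAEs. Because both are possible, sites (up to 30 of them) could apply different rules.

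**Step 3. Size.** The plan states no SAE rate or capture rate, so there is no figure to reproduce and no undercount to derive. Only two things can be shown.

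The weight of one missed patient: 1/50 = 2 percentage points at the cap in the Synopsis and Section 4.5; 1/200 = 0.5 points at the number in Section 7.1.

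An illustration, with both inputs assumed and neither taken from the documents. Let r be the true proportion of patients with a non-neurological SAE after discharge and c the probability that it is captured. Then expected patients missed = N × r × (1 − c), and expected observed proportion = r × c.

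| r | c | Missed, N = 50 | Missed, N = 200 | Observed proportion |
|---|---|---|---|---|
| 10% | 90% | 50 × 0.10 × 0.10 = 0.5 | 2 | 9% |
| 20% | 70% | 50 × 0.20 × 0.30 = 3 | 12 | 14% |
| 40% | 50% | 50 × 0.40 × 0.50 = 10 | 40 | 20% |
| any | 100% | 0 | 0 | r |

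The last row applies if sites carry out the general assessment in Section 5.8.3 and Table 1 in full.

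**The case against.** The strongest reply is that the protocol must be read as a whole. Section 5.8.3 and Table 1 require unrestricted assessment at the same time points, Table 1 schedules a focused exam that could reveal a wound infection when the visit is in person, Section 8.1 picks up SAEs behind missed visits, and Section 16.2 applies in all study phases. On this view Section 5.8.1 is an added neurological probe, placed just after the reference to the schedule of neurological assessments, and Reading B removes the conflict on SAEs.

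Much of this stands, and it rules out three stronger conclusions that a reader might draw.

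- That a non-neurological SAE reaches the database only if someone volunteers it. The general duty to assess, and the missed-visit rule, contradict this.
- That such events will be undercounted. The text supports *may be*; a site that follows every section has a duty to assess all SAEs.
- That the shortfall can be sized from the 1-5% anesthetic risk in Section 2.1. That risk (airway, aspiration, hypotension, drug reaction) is mainly peri-procedural. It falls where Table 1 marks adverse events at treatment, post-procedure and discharge or day 7, and where Section 5.6.1 reviews any event. It says little about the period after discharge.

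What the reply does not do is point to any provision that prompts for a non-neurological event or a readmission at a contact that takes place. Where one section gives the method and the others only the duty, staff are likely to follow the method.

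**Conclusion.** The point holds as an inconsistency between a stated ascertainment rule and a wider stated requirement. Non-neurological SAEs between discharge and day 180 may be under-ascertained, or ascertained differently across sites. This rests on the natural reading of Section 5.8.1 and on some sites taking that section as their working instruction. If all sites take the other reading, or carry out the general assessment in full, the loss is nil.

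The size is unknown; the ranges in the working are illustrations and not estimates. The 30-day mortality endpoint is largely unaffected, because it counts deaths from any cause and deaths also surface when the mRS is scored. AE summaries are descriptive and single-arm, so no between-arm comparison is biased. The exposure is the SAE tabulation in Section 7.5.1 and the DSMB listings. That is enough to justify correcting the wording, but it does not put the registry's main results in doubt.

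**What to change.** Reword the two sentences in Section 5.8.1 so that at every contact, whether in person, by phone or by mail, the record is surveyed and the patient or LAR is asked about:

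- any serious adverse event, of any body system;
- any hospital admission since the last contact;
- each event specified in Section 5.8.3, within its stated window.

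Keep the existing neurological and neurosurgical-procedure prompts. The 1-month contact has a 14-day tolerance and can fall as early as day 16 (30 − 14), so the 3-month contact should also ask about specified events that fell within the first 30 days.

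Merely deleting the word *neurological* is not enough. It would solicit non-serious events of every kind to day 180, although Sections 16 and 16.2 stop recording them at day 7 or discharge. The new wording should name serious events explicitly and leave that window unchanged.

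The cost is a wording change, one added CRF prompt and slightly more SAE entries at contacts already scheduled.

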5.8.2 Cross-Sectional Imaging

All scheduled CT and MR studies will be assessed by a central core lab neuroradiologist. The volume of hemorrhage will be calculated using a standard A x B x C/2 calculation. On the CT slice with the largest area of ICH, the largest diameter (A) is measured in cm. The dimension of the hemorrhage perpendicular

to the largest diameter (B), represents the second diameter. The third diameter (C) will be calculated either by multiplying the number of CT slices which depict the hematoma by the slide thickness or determined on coronal or sagittal reconstructions. The volume of hemorrhage plus peri-hematomal edema (PHE) will also be similarly calculated. Hemorrhage and hemorrhage + PHE volume as a percentage of presenting volumes will be calculated. Mass effect will be graded with each subsequent scan compared to the presentation scan (decreased, increased, no change). Intraventricular hemorrhage will be assessed on each scan and graded according to a modified Graeb score (Appendix 2). A detailed description of the imaging assessments are specified in the Imaging Interpretation Guidelines.

Scheduled imaging studies include the diagnostic/admission scan, the stability scan(s) (at least 6 hours after the diagnostic scan), CT or MR angiogram (with either the diagnostic or stability scan), Post-operative (Apollo / Artemis MIES), and the 7 day post presentation CT scan.

Table 1. Schedule of Events

ACTIVITY	SCREENING /BASELINE	STABTILITY SCAN (at least 6 hours post initial CT)	TREATMENT	Post MIES (+/-12 hours)	DISCHARGE AND /OR 7 DAYS	1 MONTH (+/-14 days)	3 MONTHS (+/-21 days)	6 MONTHS or END of study (+/- 28 days)
InformedConsent	Х							
Inclusion/ ExclusionCriteria	X							
Medical History	Х							
Focused Exam	Х	Х		Х	Х	Х	Х	Х
Standard of Care Labs	Х	Х		Х	Х			
Standard of Care CT/MR	Х	Х	X (immediately	Х	Х			
CTA or MRA	X (or at stability)	X (if not done with Baseline)	post treatment)					
NIHSS	Х	Х		Х	Х	Х	Х	Х
GCS	Х	Х		Х	Х	Х	Х	Х
mRS	Historic				Х	Х	Х	Х
EQ5D5L								Х
Pregnancy Test if childbearing potential	X	Or X						
Usual Medical Management per AHA Guidelines	Х	Х	Х	X	Х	X	X	Х
Apollo /Artemis MIES under general anesthesia within 24 hours of sx onset			X					
Adverse Events			Х	Х	Х	Х	Х	Х
All brain imaging sent to central core lab	within 48 hours of test	within 48 hours of test		within 48 hours of test	within 48 hours of test			

